**1.** Evaluate if SE+VR, compared to SE Only, enhances SE outcomes for adults with SMI. At a personlevel, we *hypothesize (H)* that SE+VR subjects, compared to SE Only subjects, will have higher employment rates (*H1*), greater improvement in job interview skills (*H2*), get jobs sooner (*H3*), and have reduced psychological distress (*H4*) by 6-month follow-up. At a system-level, we hypothesize that SE+VR will be more cost-effective than SE Only (*H5*). Exploratory Subaims: 1. Explore if VR generalizes to social skills by testing if VR training relates to enhanced social skills and longer job tenure for clients (person-level) and if SE staff spend fewer hours coaching communication at work (systems-level); 2. Explore if SE+VR staff have increased efficiency (e.g., time spent helping clients with applications and networking with employers(system-level)). **2.** Evaluate mechanisms of employment outcomes and psychological distress. Based on Corbiere's model, we *hypothesize* is that interview skills, measured independently during role-play, will mediate the effect of interview training on employment outcomes (*H*6). Exploratory Subaims: **1.** Explore if post-training levels of interviewing anxiety/self-efficacy mediate the relationship between VR training and interviewing skills and if this mediation is moderated by pre-training levels of anxiety and self-efficacy (Fig 1b); **2.** Explore if employment outcomes mediate the relationship between interviewing skills and psychological distress at 6-month follow-up.

**3.** Conduct a multilevel, multidisciplinary, and mixed-method process evaluation of VR adoption and implementation to assess the acceptability, scalability, generalizability, and affordability of VR. We will use focus groups and interviews (with clients, staff, and leaders) to identify facilitators and barriers to implementing VR. We will use budget impact analysis to estimate the cost of implementing VR at Thresholds.

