### **B. Study Design**

This is a two arm randomized, single blinded, intent-to-treat, controlled trial (RCT) with baseline and pre-test assessments, up to 10 hours of VR training, post-test assessment, and follow-up at 6 months and at 9 months. We will evaluate both person-level and system-level outcomes associated with implementing VR at Thresholds. At the person-level, we propose to evaluate if IPS+VR, as compared to IPS Only, is associated with better employment outcomes (higher employment rate, shorter time-to-employment), job interviewing skills, and greater reductions in psychological distress. Interviewing anxiety and self-efficacy will be explored as potential mechanisms in the pathway between IPS and employment. At the system-level, we propose to conduct a cost-effectiveness analysis and budget impact analysis between IPS+VR and IPS Only as well as explore whether Employment Specialists (Thresholds Staff that work one-on-one with clients) working at Thresholds spending fewer hours leading interview training is related to spending more hours completing job applications with clients and building a network of employers. We will also explore if VR generalizes to social skills at both the person-level (via job retention measures) and the system-level (using a time log completed by Employment Specialists regarding time spent coaching communication skills at work).

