8. Social Skills Performance Assessment (SSPA) (approximately 15 minutes) to assess social competence. Participants will complete two video-recorded roleplays with a research assistant.

9. Baseline Job Interview Role-Play Assessments (approximately 90 minutes): The participant will complete a typical job application, select two fictional job openings (listed below), and participate in two job interview roleplays with two trained role-play interviewers. The interviews will be videorecorded and the videos will be scored by student raters trained to a high standard of reliability and who are blinded to condition. Participants will select two jobs from the following scenarios:

1) Scenario A: The department of Public Health at the University of Illinois at Chicago is running a nation-wide study examining the effects of a newly implemented youth exercise program in elementary schools across the country. We are hiring a team of research assistants to collect and manage our study data. We look forward to building a talented team and have position openings in the following categories: Data Entry Technician, Research Assistant, and Study Coordinator. Position to which they are applying is Data Entry Technician.

**2)** Scenario B: Goldberg & Jones is a new law firm opening in downtown Chicago. G&J is a promising new law firm founded by two law students who recently graduated from Kent Law School. G&J is looking for a dedicated staff to ensure the new law firm's success. Goldberg & Jones are seeking to hire individuals for the following positions: Administrative Assistants, Mail Clerks, and Paralegals. Position to which they are applying is Mail Clerk.

**3)** Scenario C: Lakeview Hospital has provided quality care and treatment to Chicago for the past 50 years. Lakeview Hospital is currently seeking individuals to add to their dedicated team of employees for the following positions: Medical Records Clerk and Medical Receptionist. Position to which they are applying is Medical Records Clerk.

**4)** Scenario D: Goldberg & Jones is a new law firm opening in downtown Chicago. G&J is a promising law firm founded by two law students who recently graduated from Kent Law School. G&J is looking for a dedicated staff to ensure the new law firm's success. Goldberg & Jones are seeking to hire individuals for the following positions: Administrative Assistants, Mail Clerks, and Paralegals. Position to which they are applying is Paralegal.

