**D. 4. Randomization for Thresholds' Clients.** After the video-recorded pre-training role-play interviews are completed, participants will be randomized into the intervention group or the wait list control group. Block randomization tables will be created prior to the study based on computer generated blocks of six. Blocks of six will ensure nearly equal groups. Sealed envelopes containing the randomization by sequential subject entry number will be created and stored, and then opened when a participant has completed pre-randomization procedures.

**D. 5. Visits 4-9, Virtual Reality Job Interview Training Delivery.** Participants randomized to the VR training group will complete their VR training at local Thresholds location (see Appendix A), or if requested by the member (at their home). After members have completed their VR-JIT orientation and have demonstrated independence at using VR-JIT with minimal support from staff and completed at least 10 virtual interviews in lab, then study team will support the member to use VR-JIT at home if home use is requested by the member. To provide this support, the research team will show the member how to access the tool in the lab. Moreover, the member will be instructed to call the research team so that the research team can walk the member through accessing the tool once they are at home. In addition, the research team will provide the member with a instructional document so that they can access the tool from home.

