The Thresholds Research Coordinator will schedule the study participants to complete 6 two-hour sessions of VR. When participants show up for the VR training, the visit will be run the Thresholds research staff who will provide the trainee with an initial orientation to VR and then monitor the trainee's access and performance scores during the sessions. After completing the initial 6 visits, trainees will move on to complete their post-test visit. Trainees will be invited to use VR as-needed after completing the post-test visit, which will be monitored by the Team Leaders. Those participants assigned to the SE as usual group will have the option to use the VR training in the context of their regular use of Thresholds services (i.e., they will not have access to the study resources to use VR) following the completion of their participation in the study (after their 9-month follow-up phone call). At each training session, any subject who has had to travel to use the intervention will receive \$10 to reimburse them for the cost of transportation.

A note on VR delivery procedures (1/29/18): When the study initially began, Employment Specialists and Team Leaders were asked to run the VR orientation and training sessions. Due to workload expectations and coordination barriers, this responsibility was moved to the Thresholds Research Team.

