# D. 6. Visit 10 (Post-test Visit completed at Northwestern University, at a Threshold's Odgen location, or via a phone call or video-conference) will be a repeat of the following measures (see D.2. and D.3. for more details):

- 1. Brief Psychiatric Rating Scale (BPRS)
- 2. Beck Depression Inventory (BDI)
  - a. Columbia-Suicide Severity Rating Scale (C-SSRS) if triggered by BDI scores
- 3. Job-Interview Role Plays
- 4. Social Skills Performance Assessment(SSPA)
- 5. Employment History Interview (follow-up version)
- 6. Job Interview Self-Efficacy
- 7. Personal Report of Job Interview Anxiety
- 8. Intrinsic Motivation Inventory
- 9. Technology Comfort Level Questionnaire is a 6-item measure that assesses one's comfort level with computer technology (approximately 5 minutes).

In addition, VR trainees will complete the 5 item Training Experience Questionnaire (TEQ; < 5 minutes). The

Posttest Visit 10 will last approximately 150 minutes or 2 hours and 30 minutes. Participants will be paid \$50.

**D. 7. Monthly Check-in Telephone Calls for Thresholds Clients (completed via telephone) will involve a brief (<10minutes) telephone survey asking about participants' potential interview or job-related activity in the past month.** These calls will be scheduled at monthly intervals after completion of post-test until the 6-Month Follow-Up (see D. 9.), for a total of 5 calls.

D. 8. Visit 11 (6-Month Follow-Up Visit completed at Northwestern University, a Threshold's Ogden location or via a phone call or video-conference) will be a repeat of the following measures (see D.2. and D.3. for more details):

- 1. Brief Psychiatric Rating Scale (BPRS)
- 2. AUDIT-SR
- 3. DAST-10
- 4. WHOQOL-BREF
- 5. SF-36
- 6. Beck Depression Inventory
  - a. Columbia-Suicide Severity Rating Scale (C-SSRS) if triggered by BDI scores
- 7. Employment History Interview (follow-up version)
- 8. Job Interview Self-Efficacy
- 9. Personal Report of Job Interview Anxiety
- 10. Intrinsic Motivation Inventory

Participants will also complete the SF-12 health questionnaire about their physical health and the Employment History Follow-up interview that will assess how many job interviews were completed, total hours worked, how many jobs were offered (and accepted), hourly wage, type of job, jobs terminated (and why).

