**Hypothesis 5:** IPS+VR will be more cost-effective than IPS Only. To test **H5**, we will conduct a costeffectiveness analysis (CEA) to assess the short-term cost-effectiveness of IPS+VR relative to IPS Only using a societal perspective, which includes intervention costs and client costs provided by the IPS program director. Intervention costs include variable costs (e.g., time spent by ECRs) and fixed costs (e.g., costs supporting hiring, training, and coordination). Client costs will include time using VR and travel costs. We will use standard approaches to identifying and assigning unit costs for each cost component. We will use job attainment rate as our measure of effectiveness. The main step is to calculate an incremental cost-effectiveness ratio (ICER), which is defined as the difference in total costs between the IPS+VR and IPS Only groups, divided by the between-group difference in job attainment rate. Confidence intervals will be calculated around the ICER using bootstrapping and Fieller's theorem. We will conduct sensitivity analysis by deriving cost-effectiveness acceptability curves that display the probability of IPS+VR being cost-effective at various threshold values. **Exploratory (Person-Level):** To study the generalizability of VR to social skills, we will evaluate if more VR training (i.e., number of trials) is associated with a longer job tenure (number of weeks) and enhanced social skills using linear regression; covariates will include demographic, cognitive, vocational, and training characteristics that differentiate groups. **Exploratory (System-Level):** We will explore if, as a result of VR, ESPs reallocate their interviewing hours towards building larger employer networks, completing more job applications with clients, and engaging in more hours of coaching work communication with clients.

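### Generalization of VR to social skills is tested on the number of VR trials, which is not randomized; no between-arm comparison of the SSPA is specified, although both arms complete it before and after training

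*Combined protocol and SAP*

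**What the plan says.** The exploratory subaim in Section 1.0 is framed as "testing if VR training relates to enhanced social skills and longer job tenure for clients". Section 4.0 B (Study Design) puts the person-level question differently: "We will also explore if VR generalizes to social skills at both the person-level (via job retention measures"), with no mention of the SSPA there. The method is in Section 14.0, in the exploratory person-level text after Hypothesis 5: "we will evaluate if more VR training (i.e., number of trials) is associated with" longer tenure and "enhanced social skills using linear regression; covariates will include demographic, cognitive, vocational, and training characteristics that differentiate groups". The exposure is therefore the trial count. The text does not say whether IPS Only clients enter with zero trials, or up to what date trials are counted.

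The SSPA is on the list for all clients at Combined Baseline Visit 2/3 (4.0 D.3): "Social Skills Performance Assessment (SSPA) (approximately 15 minutes) to assess social competence". Randomization comes after that visit's interview role-plays (4.0 D.4): "After the video-recorded pre-training role-play interviews are completed, participants will be randomized into the intervention group or the wait list control group". At post-test Visit 10 (4.0 D.6) "Social Skills Performance Assessment(SSPA") is repeated; only the Training Experience Questionnaire there is restricted to VR trainees.

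On exposure, 4.0 D.5 schedules six two-hour sessions and allows home use if the member asks for it, after at least 10 virtual interviews in the lab and shown independence with the tool. It adds: "Trainees will be invited to use VR as-needed after completing the post-test visit". Section 4.0 F.1 describes the amount of training as a maximum of 10 hours.

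**The concern.** Whether VR improves social skills is a question about an effect. A regression on trials compares people who completed many trials with people who completed few, and those people may differ in ways that also bear on the SSPA. The regression can then show an association when VR does nothing, or miss a real effect that does not grow with the number of trials. Trials completed after T2 cannot have influenced a T2 score, yet nothing in the text excludes them.

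The covariate clause helps only in part. It selects characteristics that differ between the groups, whereas confounding of a trial count comes from characteristics that predict trials. Baseline SSPA, symptoms and motivation are measured before randomization (4.0 D.2 and D.3) but are not named in the clause.

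The stake is interpretive. Section 2.0 says that improvement in outcomes of this kind would show VR to have more than an incremental impact on employment outcomes. An association with trial count cannot carry that statement; a randomized contrast could support its social-skills part.

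**Working it through.** **The plan's own figure.** No sample size, power or alpha is given for the social-skills analysis, so there is nothing to reproduce directly. The nearest analogue is H2, which uses role-play scores from the same two visits. With d = .42, r = .7, alpha .0125 and 80 per arm, the SD of change is √(2(1 − .7)) = 0.775 and power is 0.824, against the stated 82%. The between-arm machinery for these visits is therefore already in the plan.

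**Inputs from the documents.** 160 subjects, 80 per arm; 10% missing, so 72 per arm (Section 14.0). Section 3.0 gives 180 recruits; I use the analysis plan's 160.

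**Assumed inputs.** The documents give no correlation between trials and anything else, no distribution of trials, and no pre-post correlation for the SSPA. I assume an unmeasured trait correlated a with trials and b with T2 SSPA, no VR effect, and a two-sided 5% test.

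**1. VR arm only, unadjusted.** Spurious r = a × b.
- a = b = 0.4: r = 0.16; Fisher z = 0.161; 0.161 × √77 = 1.42; P(|Z| > 1.96) ≈ 29%. With 72 trainees it is about 27%.
- a = b = 0.3: r = 0.09; 0.090 × √77 = 0.79; about 12%.

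**2. Controls entered with zero trials, unadjusted.** For trials with mean m and SD s among trainees, r = 0.5·a·b·s / √(0.5s² + 0.25m²).
- a = b = 0.4, m = 20, s = 7: r = 0.050; 0.050 × √157 = 0.63; about 10%.
- Same correlations, m = 15, s = 5: r = 0.048; about 9%.

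**3. T1 SSPA added (assumed pre-post r = .7).** The result depends on how the trait relates to T1 SSPA.
- Stable trait, equally related to T1 and T2 SSPA, a = b = 0.4, VR arm only: partial r = (0.16 − 0.16 × 0.7) / √((1 − 0.16²)(1 − 0.7²)) = 0.048/0.705 = 0.068; 0.068 × √76 = 0.59; about 9%. With controls at zero it is about 6%.
- Trait unrelated to T1 SSPA, simulated with 2,000 replicates, m = 15, s = 5:

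| a, b | VR arm only | Controls at zero | Arm ANCOVA |
|---|---|---|---|
| 0, 0 | 4% | 5% | 5% |
| .3, .2 | 12% | 7% | 5% |
| .3, .3 | 21% | 8% | 5% |
| .5, .3 | 47% | 12% | 5% |

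Adjusting for baseline SSPA therefore lowers the error when the confounder is a stable trait already visible at T1. It does not do so when the confounder acts on change.

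**4. What the randomized comparison can detect.** For an ANCOVA at two-sided .05 and 80% power, d = (1.96 + 0.84) × √(2/n) × √(1 − r²).

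| SSPA pre-post r (assumed) | n = 80 per arm | n = 72 per arm |
|---|---|---|
| .5 | 0.38 | 0.40 |
| .6 | 0.35 | 0.37 |
| .7 | 0.32 | 0.33 |
| .8 | 0.27 | 0.28 |

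**The case against.** The analysis is labelled exploratory in Sections 1.0 and 14.0, is worded as a relation, and lies outside H1 to H6 and the multiplicity-adjusted tests. Whether more practice goes with better skills is a legitimate exploratory question. Covariates are planned, cognition among them. This stands: no primary conclusion of the trial rests on this regression, and the weakness is residual confounding, not absence of adjustment.

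A reader might go further in several ways that the documents do not support.
- That the plan throws its randomized comparison away. The SSPA data are collected in both arms; the contrast is merely unspecified.
- That trials are purely self-selected. Six sessions are scheduled by the coordinator, so trials before T2 reflect attendance and pace as well as choice.
- That as-needed use adds trials for clients still without a job. Section 4.0 D.5 says only that trainees may continue.
- That 29% is the plan's error rate. It is one assumed scenario for one model.
- That the arm comparison is free of every bias. Blinded rating is stated for the interview videos but not explicitly for the SSPA. Sections 4.0 D and 8.0 D allow an abbreviated remote Visit 10 without saying whether the SSPA is part of it, so T2 scores may be missing.
- That the same repair serves job tenure. Tenure exists only for those who obtain a job, so it has no simple randomized contrast.

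**Conclusion.** The concern holds for the SSPA. The planned exposure is not randomized, the covariate rule does not target what predicts it, and a between-arm comparison is available but not written, although H2 and H4 each have one. How far the trials regression misleads cannot be fixed from the documents. With assumed correlations of 0.4 and 0.4, false positives are about 29% in an unadjusted VR-arm model and about 10% with controls at zero; a T1 SSPA adjustment lowers these to about 9% and 6% if the trait is stable. With correlations of about 0.3 the range is roughly 7% to 21% by model. The arm ANCOVA stayed near 5% in every simulated scenario, with complete data. This is an inexpensive improvement to an exploratory aim, not a flaw in the trial's main conclusions, and it leaves job tenure outside.

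**What to change.** In Section 14.0, make the main generalization analysis for the SSPA an intent-to-treat ANCOVA of T2 SSPA on randomized arm, adjusting for T1 SSPA, in all randomized clients. Handle missing T2 SSPA with the multiple imputation the plan already names, and state whether the SSPA is given and scored blind to arm at a remote Visit 10.

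Keep the trials regression as an exploratory, observational dose-response analysis within the VR arm. Count only trials completed before T2 and adjust for T1 SSPA. Report job tenure as descriptive, among those who obtain a job.

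The cost is a few lines of analysis text and one more model, with no new visits or measures.

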Alternatively, if participants are unable to attend visit 10 and/or 11 in person, the study team will schedule a series of brief phone calls in order to collect the self-reported study data by phone. In addition, the study team will offer participants the opportunity to complete their follow-up role-play assessment by means of a videoconference through BlueJeans. The BlueJeans videoconference will then be recorded by the University of Michigan research team that is approved for this study and the recordings will be stored using the previously approved methods for storing audiovisual data.

Alternatively, if the participants do not want to complete the videoconference then the participants will be offered the opportunity to complete their follow-up role-play assessment by means of a teleconference through BlueJeans. The BlueJeans teleconference will then be recorded by the University of Michigan research team that is approved for this study and the recordings will be stored using the previously approved methods for storing audiovisual data.

**D. 9. Monthly Check-in Telephone Calls for Thresholds Clients (completed via telephone) will be a repeat of procedures of the Monthly Check-in Telephone Calls for Thresholds Clients (see D. 8.).** These calls will be scheduled at monthly intervals after completion of the 6-month follow-up until the 9-month follow-up (see D. 11.), for a total of 2 calls.

D. 10. The 9-Month Follow-Up for Thresholds Clients (completed via telephone) will include only the Follow-up Employment History interview that will assess how many job interviews were completed, total hours worked, how many jobs were offered (and accepted), hourly wage, type of job, jobs terminated (and why).

The 9-Month Follow-Up Telephone Call will last approximately 10 minutes. If participants complete at least one of the two check-in calls between the 6-Month and 9-Month Follow-Up calls, they will be paid \$10 by Thresholds after the completion of the 9-Month Follow-Up call.

**D. 11. Participation Complete.** If a Thresholds client becomes employed prior to the 6-month follow-up call, they will still participate in monthly check-in phone calls and the 6-month follow-up. Their participation in the study will then be complete after completing the 6 month visit.

If the participant becomes employed between the 6- and 9-month follow-up calls, the participant will be asked additional questions on their next check-in call, which will be their last check-in.

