### F. Participant Timelines

**F. 1. Thresholds Clients.** Individuals receiving mental health services at Thresholds who are enrolled in the effectiveness trial will participate in the study for a period of 9 months. Over the first month, they will complete a series of study measures and if randomized to the intervention group, this participation will include up to 10 hours of virtual reality training. After the first month, the participants randomized to the training group are

welcome to use the training as-needed, which will be monitored using their ID number. Then approximately 6 months after participants complete their post-test visit, they will be invited to complete their 6-month follow-up visit. Approximately 3 months after the 6-month visit, participants will be contacted via phone for a 9-month follow-up interview. Their participation in the study will end at this time.

After 1/3 of the effective trial participants have completed their intervention training (and before the completion of the 6 month follow-up) 20 VR trainees will be recruited to participate in a series of focus groups.

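### The exploratory job-tenure analysis applies linear regression to weeks of tenure with no rule for jobs still held at last contact, so the estimate is biased by right-censoring, in a direction and size that depend on inputs the plan does not give

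*Combined protocol and SAP*

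**What the plan says.** The sub-aim is exploratory. Section 1.0 words it as "Explore if VR generalizes to social skills by testing if VR training relates to enhanced social skills and longer job tenure for clients". Section 14.0 (Data Analysis Plan for Aims 1 & 2, Exploratory, Person-Level) gives the method: test whether the number of VR trials "is associated with a longer job tenure (number of weeks) and enhanced social skills using linear regression", with covariates that differentiate the groups. It does not say how a job still held at last contact enters the outcome, or whether clients who never work are included. Multiple imputation is planned for missing data in longitudinal analyses; ongoing jobs are not mentioned.

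Follow-up depends on employment (section 4.0, D.11):

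- Job found before 6 months: "they will still participate in monthly check-in phone calls and the 6-month follow-up", and then "Their participation in the study will then be complete after completing the 6 month visit".
- Job found between 6 and 9 months: "the participant will be asked additional questions on their next check-in call, which will be their last check-in".
- No job found: participation runs to the 9-month telephone call.

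Section 4.0 F.1 says instead that clients in the trial "will participate in the study for a period of 9 months". Section 4.0 B lists "follow-up at 6 months and at 9 months" as design time points.

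The employment interviews at 6 months (D.8) and 9 months (D.10) record jobs that ended and the reason. A Cox model is planned for time-to-employment (H3), but not for tenure.

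**The concern.** A client who is still working when contact stops has a tenure known only to exceed the weeks seen so far. That lower limit equals last contact minus hire date, so it reflects how early the job was found as much as how long it would last. A least-squares model has no place for this information. It takes each recorded number of weeks as the outcome, unless a rule says otherwise, and none does.

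The clients with the longest jobs lose the most weeks, which pulls a real association towards zero. In the other direction, if VR leads to earlier hiring, as H3 proposes, the observation window opens earlier and recorded tenure rises with no true effect on how long jobs last. A null or a positive result could each be an artefact. Tenure is one of two person-level outcomes for whether VR generalizes beyond the interview; the other is social skills.

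**Working it through.** **Figures in the plan.** No mean tenure, effect size or power is given for this analysis, so there is no figure of its own to reproduce. The H3 hazard used below checks as a weekly rate: −ln(0.80)/26 = 0.00858, and 1 − exp(−0.0085 × 26) = 0.198.

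**Inputs.**

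- Hiring: 25% by 26 weeks (control rate under H1) at a constant hazard, h = −ln(0.75)/26 = 0.01106 per week.
- Last contact: T = 30 weeks, from about one month of visits plus about six months after post-test (F.1), 4 + 26.
- Job length: exponential with mean m. This is an assumption; m is varied from 5 to 40 weeks and then doubled.

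**Formula.** For clients hired before T, observed weeks = min(job length, T − hire week). The share of jobs still held at T is

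c = h·e^(−T/m)·(e^((1/m−h)T) − 1) / [(1/m − h)(1 − e^(−hT))],

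and the mean observed tenure is m(1 − c). For m = 20: c = 0.01106 × 0.2231 × 2.216 / (0.03894 × 0.2825) = 0.497, so the mean is 20 × 0.503 = 10.05 weeks.

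| True mean (weeks) | Still held at T | Observed mean | Visible gain | Share of true gain |
|---|---|---|---|---|
| 5 → 10 | 15%, 29% | 4.26, 7.06 | 2.8 of 5 | 56% |
| 10 → 20 | 29%, 50% | 7.06, 10.05 | 3.0 of 10 | 30% |
| 20 → 40 | 50%, 69% | 10.05, 12.43 | 2.4 of 20 | 12% |
| 40 → 80 | 69%, 83% | 12.43, 13.98 | 1.5 of 40 | 4% |

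**Standardised effect.** The cap also shrinks the spread. The true doubling is m/√((m² + 4m²)/2) = 0.63. In the 20-to-40 case the simulated observed SDs are 7.7 and 8.4, pooled 8.06, so 2.38/8.06 = 0.30, about half. In the 5-to-10 case 0.53 of 0.63 remains.

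**The planned exposure.** The table contrasts two populations, whereas the plan regresses on number of trials. A second simulation used that form: 26-week window, tenure 1.5 times longer per SD of trials, two-sided 0.05, and 42 employed clients in the VR arm (80 × 0.53, from H1). The slope in weeks keeps about 59%, 35%, 15% and 5% of its true size at means of 5, 10, 20 and 40 weeks. Power of linear regression against Cox with ongoing jobs censored is 50% v 58%, 37% v 51%, 21% v 39% and 13% v 25%. With 29 employed clients (80 × 0.36, from H3) it is 34% v 41%, 26% v 37%, 16% v 27% and 10% v 18%.

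**Upward bias.** Job-finding hazards were set to 0.0085 and 0.017 per week (H3, ratio 2.0), with no true tenure effect and a 26-week window. For means of 5 to 40 weeks, the employed-only comparison shows a spurious gain of 0.07 to 0.37 weeks. Coding never-employed clients as 0 weeks raises it to 0.7 to 1.9 weeks (standardised 0.24 to 0.30).

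**Longer contact.** If clients hired by week 30 are followed to week 43 (4 + 39), c is multiplied by e^(−13/m). For m = 20, 0.497 × 0.522 = 0.260, mean 14.81; for m = 40, 0.689 × 0.723 = 0.498, mean 20.08. The visible gain rises from 2.4 to 5.3 of 20 weeks.

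**Later hires.** The table leaves out clients hired between 6 and 9 months. With monthly calls, their observable tenure is at most about a month.

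**The case against.** The plan gives this analysis one clause, labels it exploratory and claims no power for it. Four points on that side stand.

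- A reader might infer that the plan counts ongoing jobs as finished. It does not say so. Job endings are recorded at D.8 and D.10, so a censoring flag can be built; what the text shows is that no rule is given.
- A reader might infer that a real tenure benefit would be largely hidden. That needs a mean tenure the documents do not state. In the 26-week simulation with tenure 1.5 times longer, more than half of the gain in weeks is lost only above a mean of about 6 to 7 weeks; at 2 to 4 weeks, 64% to 85% remains. Raw weeks also overstate the loss of signal, because the spread shrinks too.
- Section 4.0 B might be read as promising both follow-ups to everyone. It only lists time points. The clear conflict is between D.11 and F.1.
- A censored-data model recovers only part of the lost power.

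None of this makes linear regression suitable. Recording job endings helps only if the model uses them, and the stated model does not. Exploratory status limits how much the point matters; it does not remove the bias.

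**Conclusion.** The concern holds in a limited form. Tenure is right-censored by the contact rule in D.11, and linear regression on weeks, as written, gives a biased estimate. The 4% to 56% range rests on exponential job lengths, a constant hiring hazard, last contact at week 30 and assumed mean tenures; none of the tenure inputs comes from the documents. The direction is not fixed: censoring pulls a true association towards zero, while earlier hiring pushes the estimate up, most strongly if never-employed clients are coded 0.

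A reader might take this as a threat to the trial's main conclusions. The documents do not support that. Tenure enters none of H1 to H6, H3 already uses a Cox model, and social skills are assessed directly by the SSPA. The point is worth correcting because the remedy is nearly free and job end dates that were never collected cannot be recovered by analysis.

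**What to change.** 1. In section 14.0, define tenure from hire date to job end. Among clients who obtain a job, analyse it with a Cox or accelerated-failure-time model on number of VR trials, censoring jobs that are ongoing at the last confirmed working date.
2. State that never-employed clients do not enter this model and are not coded as 0 weeks.
3. Reconcile D.11 with the 9-month participation in F.1. Keeping the two existing check-in calls (D.9) and the 9-month call (D.10) for employed clients would reduce censoring.

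Items 1 and 2 cost SAP wording only, since the follow-up interviews already record ended jobs. Extending contact under item 3 would add up to three short calls and the existing $10 payment per employed client.
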